8.2.2 Efficacy Assessments

8.2.2.1 Radiologic Imaging Assessment

Radiographic assessments will be obtained as scheduled in Section 1.3 irrespective of cycle duration including dose delays and treatment discontinuation.

For subjects developing COVID19 during screening period following screening imaging, consider repeating CT of chest imaging following resolution.

Standard radiological assessments should take place until clinically significant disease progression or deterioration, withdrawal of consent, or start of new anticancer therapy. Every assessment must include the chest, abdomen, and pelvis, all other known sites of disease and magnetic resonance imaging (MRI) of the brain if a subject has signs or symptoms suggestive of CNS metastases. The MRI/CT can be obtained earlier if clinical deterioration necessitates an earlier scan at the discretion of the managing physician. The same contrast and modality used at screening should be used for all subsequent assessments. ^{99m}Tc-MDP (^{99m}technetium methylene diphosphonate) bone scan is required for each radiologic imaging and tumor assessment.

Tumor burden assessments will be performed per PCWG3 guidelines (Sections 11.8 and 11.9). To confirm soft tissue disease progression, a second MRI/CT scan must be performed at least 4 weeks after the first detection of soft tissue disease progression. Responses (partial response [PR] and complete response [CR]) require confirmation by a repeat consecutive assessment at least 4 weeks after the first detection of response as measured by RECIST 1.1. Planar bone scintigraphy must be performed using

conventional ^{99m}technetium methylene diphosphonate radionuclide (^{99m}Tc-MDP) or other equivalent ^{99m}Tc-labeled radiotracers. Confirmation of bone disease progression by bone scan should be performed per PCWG3 guidelines. Disease progression based on both MRI/CT and bone scans will be used in radiographic progression endpoints (eg, radiographic PFS) evaluation. Soft-tissue progression based on MRI/CT scan will be used in response endpoints (eg, objective response and DOR) evaluation. Treatment beyond confirmed tumor progression may be allowed as per PCWG3 guidelines (Section 11.8; Scher et al, 2016). Refer to the imaging manual for details on imaging assessments.

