* Stable Disease (SD):	Neither sufficient shrinkage to qualify for PR nor sufficient increase to qualify for PD, taking as reference the smallest sum of diameters since the treatment started.

Evaluation of Non-target Lesions

* Complete Response (CR):	Disappearance of all non-target lesions and normalization of tumor marker level. All lymph nodes must be non-pathological in size (< 10 mm short axis).
* Non-Complete Response (CR)/Non-Progressive Disease (PD):	Persistence of one or more non target lesion(s) or/and maintenance of tumor marker level above the normal limits.
* Progressive Response (PD):	Unequivocal progression of existing non-target lesions and/or appearance of one or more new lesions. ¹

¹ To achieve “unequivocal progression” on the basis of the non-target disease, there must be an overall level of substantial worsening in non-target disease such that, even in presence of SD or PR in target disease, the overall tumor burden has increased sufficiently to merit discontinuation of therapy. A modest “increase” in the size of 1 or more non-target lesions is usually not sufficient to qualify for unequivocal progression status.

Evaluation of Overall Response

The best overall response is the best response recorded from the start of the study treatment until the end of treatment (EOT) or disease progression/recurrence (taking as reference for progressive disease [PD] the smallest measurements recorded since the treatment started).

In general, the subject's best response assignment will depend on the findings of both target and non-target disease and will also take into consideration the appearance of new lesions.

Time Point response: Subjects With Target (± Non-target) Disease

Target Lesions	Non-target Lesions	New Lesions	Overall Response
CR	CR	No	CR
CR	Non-CR/non-PD	No	PR
CR	Not evaluated	No	PR
PR	Non-PD or not all evaluated	No	PR
SD	Non-PD or not all evaluated	No	SD
Not all evaluated	Non-PD	No	NE
PD	Any	Yes or No	PD
Any	PD	Yes or No	PD

CR = complete response; NE = Not evaluable; PD = progressive disease; PR = partial response; SD = stable disease.

Time Point Response: Subjects With Non-Target Disease Only

Non-target Lesions	New Lesions	Overall Response
CR	No	CR
Non-CR/non-PD	No	Non-CR/non-PD [‡]
Not all evaluated	No	NE
Unequivocal PD	Yes or No	PD
Any	Yes	PD

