The subject's best response assignment will depend on the findings of both target and non-target disease and will also take into consideration the appearance of new lesions and confirmation of response. Confirmation of progressive disease is not required. Best overall response (BOR) will be based on all post-baseline disease assessments that occur prior to the initiation of subsequent anticancer treatment. At least 7 weeks from the first dose of IP must elapse without radiological disease progression to meet the minimum criteria for SD duration in order to assign a best overall response of SD. In general, subjects not classifiable under the RECIST 1.1

Date: 24 March 2023 Page 22 of 53

response categories due to inadequate data or early death will be classified as non-evaluable (NE) for BOR but will be counted in the denominator of all response rate calculations. The BOR will depend on the findings from MRI/CT scans. BOR per RECIST 1.1 has the following possible categories: complete response (CR), partial response (PR), stable disease (SD), progressive disease (PD) or not evaluable (NE). The rules for deriving the BOR are detailed in Appendix D.

Disease control rate (DCR)

DCR is defined as the **proportion** of subjects with a best overall response of confirmed response (CR/PR) or SD as per RECIST 1.1.

Duration of Response (DOR) per RECIST 1.1

DOR is defined as the time from the date of an initial objective response per RECIST 1.1 to the earlier of progressive disease per RECIST 1.1 or death for subjects with an objective response. **DOR** will be censored following the same censoring strategy as radiographic progression-free survival as detailed in Appendix B.

Objective Response (OR) per RECIST 1.1

OR is defined as best overall response of PR or CR per RECIST 1.1, confirmed by an assessment at least 4 weeks later. Subjects who do not experience a PR/CR or do not have any follow-up tumor assessments will be regarded as non-responders.

Objective Response Rate (ORR)

ORR is defined as the **proportion** of subjects with a best overall response of **confirmed** CR or PR per RECIST 1.1.

Overall Survival (OS)

OS is defined as the time from the start of treatment until event of death due to any cause. Subjects still alive will be censored at the date last known to be alive. If the date last known to be alive is after the date that triggers the analysis (i.e., the data cut-off date), the subject will be censored at the data cut-off date.

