Appendix B. Censoring Rules for Radiographic Progression-free Survival

Table 14-2. Censoring Rules for Radiographic Progression-free Survival

Situation up to DCO/EOS	Date of Event or Censor	Outcome
PD	Date of first detection of PD	Event
No PD, but death recorded	Date of death	Event
Subject has no post-baseline radiographic tumor assessment and a vital status of alive or unknown	First dose date of IP	Censor
Subject does not show progression according to RECIST 1.1 or bone scan using PCWG3 criteria	Date of the last scan	Censor
Subject remains on study treatment and prior scans do not show radiographic progression	Date of the last scan showing no disease progression	Censor
Subject receives subsequent therapy known or intended for prostate cancer during the study prior to the radiographic progression	Date of the last scan showing no disease progression	Censor
Subject misses >= 2 consecutive planned radiographic scans (18 weeks) or has >= 2 consecutive unreadable scans (18 weeks)	Date of the last scan showing no disease progression	Censor

Date: 24 March 2023 Page 48 of 53

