C11			NE, No furth	ner evaluat	ions	NE
C12	PR	Yes	CR, PR	-	Yes	PR
C13			CR, PR	-	No	SD
C14			SD	-	-	SD
C15			PD	-	-	SD
C16			NE, No furth	ner evaluat	ions	SD
C17		No	CR, PR	-	Yes	PR
C18			CR, PR	Yes	No	SD
C19			CR, PR	No	No	NE
C20			SD	Yes	-	SD
C21			SD	No		NE
C22			PD	-	-	PD
C23			NE, No furth	ner evaluat	ions	NE
C24	SD	Yes	CR, PR, SD evaluation	, PD, NE, ı	no more	SD
C25		No	CR, PR, SD	Yes	-	SD
C26			CR, PR, SD	No		NE
C27			PD	-		PD
C28			NE, No furth	ner evaluat	ions	NE
C29	PD		-			PD
C30	NE	-	NE, No furth	ner evaluat	ions	NE
C31		-	CR, PR, SD	Yes	-	SD
C32		-	CR, PR, SD	No	-	NE
C33		-	PD	_	-	PD
~ -						

CR = complete response, PR = partial response, SD = stable disease, PD = progressive disease, NE = not evaluable.

*If a CR is truly met at first time point, then any disease seen at a subsequent time point, even disease meeting PR criteria relative to baseline, makes the disease PD at that point (since disease must have reappeared after CR). Best response would depend on whether minimum duration for SD was met. However, sometimes 'CR' may be claimed when subsequent scans suggest small lesions were likely still present and in fact the patient had PR, not CR at the first time point. Under these circumstances, the original CR should be changed to PR. A CR may also be followed by a PR when the target lesion assessment

Product: Tarlatamab (AMG 757)
Protocol Number: 20200040
Date: 24 March 2023
Page 51 of 53

is CR and the non-target lesion assessment is NE. In both of these situations, the best response is PR.

Table 14-4. BOR Derivation Step

Step 1. Derive Confirmed_BOR at each visit

Derive Confirmed BOR at each visit:

- At Visit 1: Use the Visit 1 scan result and refer to Table 14-3 to derive Confirmed BOR.
- ii) At Visit 2 onward:
 - (a) If current visit is CR: Find last scan that is not NE and at least 28 days before current visit. If current visit is PR: Find last scan that is not NE or SD and at least 28 days before current visit. Derive BOR temp as below:

Last scan	Current	BOR_temp
CR	CR	CR
PR	CR	PR
PR	PR	PR

- (b) If none of above fits, find last scan reference Table 14-3 to derive BOR_temp.
- iii) Current visit Confirmed_BOR = best of (BOR_temp, last visit confirmed_BOR). Use rule CR > PR > SD > PD > NE

Step 2. Derive Interim BOR at last visit prior to DCO

Step 2. Derive into	erini_BOK at last visit prior to DCO	
For subjects who discontinue	For subjects with potential for more assessment	

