tumor assessment (i.e. had PD,	(i.e. no PD, next therapy, or end of study),	
next therapy, or end of study):	unconfirmed PR/CR can be considered	
	responders.	
Assign Interim_BOR =	If any scan is CR and haven't got the	
Confirmed_BOR	opportunity to receive next scan, then	
	Interim_BOR = CR.	
	If any scan is PR and haven't got the	
	opportunity to receive next scan, then	
	Interim_BOR = PR.	
	Else, Interim_BOR = Confirmed_BOR at the	
	latest scan.	

Date: 24 March 2023 Page 52 of 53

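### Best overall response is not cut off at first progression, so later scans can create a confirmed response; confirming a PR across stable-disease scans is a separate departure from the protocol that SAP Section 10 does not list

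*SAP*

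**What the plan says.** **Window for best overall response (BOR).** SAP Section 5.3: "Best overall response (BOR) will be based on all post-baseline disease assessments that occur prior to the initiation of subsequent anticancer treatment". The only cut-off is new anticancer therapy. The same paragraph adds "Confirmation of progressive disease is not required", so a single PD assessment counts as PD. For a BOR of SD it asks that "At least 7 weeks from the first dose of IP must elapse without radiological disease progression".

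**Derivation.** SAP Appendix D ranks CR above PR, SD, PD and NE in that order. Table 14-4 Step 1 derives a value at each visit and carries the best forward: "Current visit Confirmed_BOR = best of (BOR_temp, last visit confirmed_BOR". For a current PR, Step 1(a) looks back past NE and SD scans to the last remaining scan at least 28 days earlier. Step 2 names progression as a reason for having discontinued ("tumor assessment (i.e. had PD"), but then copies the Step 1 result.

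**Protocol.** Appendix 8 defines BOR as the best response "recorded from the start of the study treatment until the end of treatment (EOT) or disease progression/recurrence". Section 8.2.2.1 requires CR and PR to be confirmed at the next assessment in sequence, at least 4 weeks later. The Appendix 8 confirmation table maps PR followed by SD to SD.

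**PR confirmation in the SAP.** Appendix D allows any number of SD scans between a PR and its confirmation, and gives PR, SD, SD, SD, PR as a confirmed PR.

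**Dating of PD.** SAP Table 14-2 uses "Date of first detection of PD" as the rPFS event date. SAP Section 5.3 runs duration of response (DOR) from the initial response to PD or death and applies the same censoring strategy.

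**The concern.** There are two separate problems.

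1. With no stop at PD and a running best, two favourable scans after progression override the PD. That conflicts with protocol Appendix 8. It also conflicts with the SAP: Table 14-3 row C29 ends at PD, Step 2 treats PD as the end of assessment, and Section 5.3 sets a progression-free minimum for SD that Step 1 does not check.
2. Confirming a PR across SD scans differs from the protocol's consecutive rule, and SAP Section 10, which lists changes from the protocol, mentions only the interim analysis sets.

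Scans after the first PD are built into the design. Protocol Section 8.2.2.1 says "a second MRI/CT scan must be performed at least 4 weeks after the first detection of soft tissue disease progression" and allows for treatment beyond confirmed progression. Protocol Section 8.1.4 continues imaging, for subjects who stopped treatment for other reasons, until PD is confirmed.

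The stake is the reported ORR, DCR and DOR. A subject could be a confirmed responder in one table and an earlier rPFS event in another.

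**Working it through.** **Step 1: apply Tables 14-3 and 14-4 to PD, PR, PR** (8-week scans, days 56, 112, 168).

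- Day 56: PD, row C29, value PD.
- Day 112: PR. The look-back finds the PD on day 56, which is not a confirming pair, so Table 14-3 applies with PD as the last scan: row C29, PD. Best of (PD, PD) = PD.
- Day 168: PR. The look-back finds the PR on day 112, 56 days earlier. PR then PR = PR. Best of (PR, PD) = **PR**.

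**Step 2: other sequences, coded literally.** Scans are every 56 days unless days are given.

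| Scans | SAP as written | Stopped at first PD |
|---|---|---|
| PD, PR, PR | PR | PD |
| PD (d56), PR (d84), PR (d112) | PR | PD |
| PD, PD, PR, PR | PR | PD |
| SD, PD, PR, PR | PR | SD |
| PR, PD, PR, PR | PR | SD |
| PD, SD, SD | SD | PD |
| PD (d42), SD (d70), SD (d112) | SD | PD |
| PD, PR | PD | PD |
| PD, SD | PD | PD |
| PR, PD, PR | SD | SD |

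PD, PD, PR, PR shows that the problem does not depend on the PD being unconfirmed. The last three rows show that, on scheduled scans, one favourable scan after PD is not enough; two are needed.

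**Step 3: SD gap.** PR, SD, PR and PR, SD, SD, SD, PR are both PR under the SAP, with or without a stop at PD. Under the protocol's consecutive rule both are SD. The issue is therefore separate from the PD cut-off. On 8-week scans, the SAP's own example confirms a week-8 PR at week 40, which is 40 - 8 = 32 weeks later.

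**Step 4: DOR.** With PD dated at first detection, DOR = PD week - response week.

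- PD week 8, PR from week 16: 8 - 16 = -8 weeks.
- PD week 8, PR from week 12: 8 - 12 = -4 weeks.

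**Step 5: size on ORR.** The plan's figure is in protocol Section 9.2: 40 subjects and a 20% response rate give an expected 95% CI of 9% to 36%. The Clopper-Pearson lower limit is the 2.5th percentile of Beta(x, n - x + 1) and the upper limit is the 97.5th percentile of Beta(x + 1, n - x).

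- x = 8: 20.0%, 9.1 to 35.6. This reproduces the plan.
- x = 9: 22.5%, 10.8 to 38.5.
- x = 10: 25.0%, 12.7 to 41.2.

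Each added responder is 1/40 = 2.5 points. One and two added subjects are illustrations; the documents give no frequency.

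**The case against.** **The SAP plainly intends a PD cut-off.** Row C29, Step 2 and the 7-week sentence all point that way, so this may be only a missing clause. The intent is likely, but Step 2 takes over the untruncated Step 1 value, and a programmer who follows the specification gets the results above.

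**The patterns may be rare.** The required second scan is not sufficient alone; a further scan without new therapy is needed. A persisting new lesion keeps the timepoint response at PD. SAP Section 5.1 ends follow-up imaging at progression without requiring confirmation, unlike protocol Section 8.1.4. All this stands, and it is why no frequency is claimed.

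**The day-42 example is excluded by the SAP's text.** Section 5.3 does exclude it, but Step 1 does not apply that sentence. A PD at the scheduled week-8 scan (days 49 to 63 with the window) would not be caught by it in any case.

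**Progression in Appendix 8 might mean confirmed PD.** Protocol Section 8.2.2.1 does ask for a confirming scan. On that reading PD, PR, PR no longer conflicts with the protocol, but PD, PD, PR, PR still does.

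**DOR could run to the next PD.** Then it is not negative, but the rPFS event still precedes the response.

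**The SD exception is openly written, and the SAP is based on amendment 6.** Both are true. The supplied protocol is amendment 7. Its log lists only the non-target lesion table as changed in Section 11.8, but it is not a complete record: it does not mention the fall from about 100 subjects in the SAP to about 60. Amendment 6 may have read differently, though nothing supplied shows that it did.

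**Conclusion.** The concern holds in both parts. As written, SAP Section 5.3 and Table 14-4 Step 1 can turn a subject who has progressed into a confirmed responder or a case of disease control, contrary to protocol Appendix 8 and to other parts of the SAP. Appendix D's confirmation across SD differs from the supplied protocol and is not listed in Section 10. That rule can only raise ORR and does not make DOR negative.

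The size is 2.5 ORR points per affected subject if all 40 subjects in the group are in the denominator. The number affected is unknown. The negative DOR rests on PD being dated at first detection. These are secondary endpoints and no hypothesis is tested. No claim is made about NoGo, which both documents restrict to non-binding interim futility. The point should be fixed before the analysis, because the correction is small and ORR, DCR and DOR are among the main reported efficacy results.

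**What to change.** - In SAP Section 5.3 and Table 14-4 Step 1, restrict BOR to assessments up to and including the first RECIST 1.1 PD and before new anticancer therapy. Using the first PD follows the SAP's statement that PD need not be confirmed; the protocol's confirmed-PD wording should be reconciled with it. State also whether scans after end of treatment count, since Appendix 8 names that limit.
- Align the PR confirmation rule, including intervening SD and NE scans, with protocol Section 8.2.2.1 and the Appendix 8 confirmation table, or declare the departure in SAP Section 10 with a reason.
- Report post-PD responses and PR-SD-PR responses only as labelled sensitivity analyses.

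The cost is a few lines of SAP text and a small programming change. ORR and DCR may be slightly lower, and a genuine late response after an early apparent progression would appear only in the sensitivity analysis.

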6.1 Full Analysis Set

The Full Analysis Set is the same as the Safety Analysis Set as described in Section 6.2.

Date: 24 March 2023 Page 25 of 53

6.1.1 Primary Analysis Set

Not applicable to the study.

6.2 Safety Analysis Set

The Safety Analysis Set **is defined as** all subjects who received at least 1 dose of tarlatamab. The analysis of all safety and efficacy endpoints, unless noted otherwise, will be conducted on the Safety Analysis Set.

6.3 Per Protocol Set(s)

Not applicable to the study.

6.4 Health-related Quality-of-Life or Health Economics Analyses Set(s) Not applicable to the study.

6.5 Pharmacokinetic/Pharmacodynamic Analyses Set(s)

The PK Analysis Set contains all subjects who received at least 1 dose of tarlatamab and have at least 1 PK sample collected. These subjects will be evaluated for PK analysis unless the number of data points required for analysis is not enough, or significant protocol deviations have affected the data, or if key dosing or sampling information is missing. For all study parts, PK Analysis Set will be used to conduct the analysis of PK data, unless otherwise specified.

6.6 Interim Analyses Set(s)

At interim analysis with cut-off determined, the DLT data will be analyzed based on DLT Analysis Set, PK parameters will be analyzed based on PK Analysis Set, interim efficacy analysis will be performed on the Interim Efficacy Analysis Set. All other data will be reported using Safety Analysis Set, unless otherwise specified.

The Interim Efficacy Analysis Set consists of all subjects in the Safety Analysis Set who have had the opportunity to be followed for at least 9 weeks starting from **study** day 1. Subjects who stopped disease assessment prior to 9 weeks will be included in this analysis set if the data cutoff is at least 9 weeks after their first dose date.

6.7 Study-specific Analysis Set(s)

6.7.1 DLT Analysis Set

DLT Analysis Set is defined as all subjects from the Safety Analysis Set who are DLT evaluable **as defined in section 5.2**. For each part of the study, the analysis of DLT will be conducted on the DLT Analysis Set.

Date: 24 March 2023 Page 26 of 53

6.7.2 RECIST 1.1 Evaluable by Central Reviewer Analysis Set (/by Investigator Assessment)

RECIST 1.1 Evaluable by Central Reviewer Analysis Set is defined as all subjects that are enrolled, received at least 1 dose of tarlatamab, have measurable baseline disease per RECIST 1.1 with PCWG3 modifications as assessed by central reviewer and had the opportunity to be followed for at least 9 weeks starting from study day 1. Subjects who stopped disease assessment prior to 9 weeks will be included in this analysis set if the data cutoff is at least 9 weeks after their first dose date. This analysis set will be used for RECIST 1.1 related endpoints assessed by central reviewer for interim, primary and final analyses.

RECIST 1.1 Evaluable by Investigator Assessment Analysis Set is similarly defined using RECIST 1.1 with PCWG3 modifications as assessed by an investigator. This analysis set will be used for RECIST 1.1 related endpoints assessed by investigator for interim, primary and final analyses.

Date: 24 March 2023 Page 27 of 53

7. Planned Analyses

The following interim, primary and final analysis are planned.

7.1 Interim Analysis and Early Stopping Guidelines

Safety data will be reviewed on an ongoing basis. During dose exploration and formally during DLRMs, Amgen, in consultation with the site investigators, will review all available cumulative data by dose level prior to making dose escalation or dose de-escalation recommendations. Adverse events and DLTs observed in all subjects will be evaluated continually and fully integrated into all DLRMs and considered in all enrollment and dosing decisions.

For DLRMs, data will be subject to ongoing checks for integrity, completeness and accuracy; however, there is no requirement to resolve outstanding data issues ahead of the snapshot. All available data up to and including the data cut-off date will be included in the analysis based on an "as-is" snapshot of the database without data locking.

During dose expansion, Amgen will conduct evaluations of the ongoing grade 4 or higher treatment-related adverse event rate to assess if the threshold for possible early trial termination has been reached. If this threshold is met in either group in Part 2, enrollment to both dose expansion groups will be halted pending review of safety data by the DLRT. After receiving the DLRT recommendation, Amgen will choose to take one of the following actions.

- 1) Terminate the trial
- 2) Resume Dose Exploration with a schedule as outlined in the protocol and recommended by the DLRT.
- 3) Amend the protocol to potentially improve the benefit/risk for subjects (e.g., increase safety monitoring, modify dose/schedule, mandate premedication)
- 4) Continue dose expansion without any changes.

Date: 24 March 2023 Page 28 of 53

The stopping rules use a Bayesian approach proposed by Thall and colleagues (Thall et al, 1995) to terminate the study if the posterior probability that the grade 4 or higher treatment-related adverse event rate is greater than 20% is > 80%. The stopping boundaries assume a prior distribution of Beta (0.40, 1.60) as presented in Table 7-1 and the operating characteristics with pre-specified batch size of 10 new subjects per batch are presented in Table 7-2. The operating characteristics in Table 7-2 provide the probability of stopping the trial early for given hypothetical true rate of grade 4 or higher treatment-related adverse events, whereas the stopping criteria in Table 7-1 are based on situations where the empirical evidence would result in a posterior probability of \geq 80% that the true grade 4 or higher treatment-related adverse event rate is \geq 20%.

Table 7-1. Stopping Boundary with Posterior Probability of 80% and Grade 4 or Higher Treatment-related Adverse Event Limit of 20%

Number of Subjects	Stop Subjects if Observing This Many Grade 4 or Higher Treatment-related Adverse Events
10	≥ 4
20	≥ 6
30	≥ 9
40	≥ 11
50	≥ 13
60	≥ 15
70	≥ 18
80	Dose Expansion Complete

Table 7-2. Operating Characteristics with Batch Size of 10 Subjects

True Grade 4 or Higher Treatment-related Adverse Event Rate	Probability of Early Stopping of Dose Expansion	Average Dose Expansion Sample Size
0.10	2.0%	78.6
0.15	11.9%	73.1
0.20	37.2%	60.3
0.25	69.8%	43.3

Date: 24 March 2023 Page 29 of 53

0.30	91.0%	29.1
------	-------	------

Interim futility analyses (non-binding) will be performed in a continuous manner using Bayesian predictive probability (Lee & Liu, 2008). Interim futility analyses will begin in each group after approximately 20 subjects have been treated and have a minimum potential follow-up of 9 weeks. Interim futility analyses will be based on the Interim Efficacy Analysis Set. Following this initial interim futility analysis, subsequent interim futility analyses will be performed after every 10 subjects in each group have reached the data cutoff criteria, until all subjects are enrolled and evaluated.

An additional interim analysis will be performed once each subject in this group either completes at least 6 months on study or withdraws from the study. For interim analyses a response is defined as either a confirmed or unconfirmed CR or PR as per RECIST 1.1. For the final analysis, a response is defined as a confirmed CR or PR as per RECIST 1.1.

For the interim analysis, data will be subject to ongoing checks for integrity, completeness and accuracy with the expectation that outstanding data issues for selected CRF pages as deemed critical by the study team are resolved ahead of the snapshot to the extent possible. All available data up to and including the data cut-off date will be included in the analysis based on an "as-is" snapshot of the database with targeted data cleaning without data locking.

The Target Value (TV) is set to demonstrate a 18% increase in ORR (i.e., TV = 30%) over the benchmark 12% ORR. For Part 2, at final analysis:

 NoGo criteria will be met if the probability that the true ORR exceeds the pre-specified TV of 30% is less than 5% (i.e., NoGo: P[ORR > TV] < 5%).

Given the existing observed data during the continuous monitoring stage, the Bayesian predictive probability is obtained by calculating the probability of reaching a NoGo decision should the treatment group be enrolled and evaluated to the maximum planned final sample size of 40 in each group in Part 2. Further enrollment to the respective group in Part 2 may be terminated if futility criteria are met. Notice the NoGo criteria is for interim futility analysis purpose only.

 Futility is met if it is predicted that there is a high probability of reaching a NoGo decision upon full enrollment of 40 subjects in the respective group in Part 2

Date: 24 March 2023 Page 30 of 53

given the existing observed data (ie, predictive probability of a NoGo decision > 95%).

The decision matrix for continuous monitoring of ORR is provided in Figure 7-1 assuming a prior distribution of Beta (1, 1). For example, given TV of 30%, 3 or fewer observed responders after 30 subjects have reached the data cutoff criteria would trigger stopping enrollment claiming futility due to a high probability of reaching a NoGo decision upon full enrollment to 40 subjects in the respective group, given the existing observed data in that group.

Figure 7-1. Decision Matrix for Continuous Monitoring of ORR

Operating characteristics of this continuous monitoring method are presented in Table 7-3 and are based on 100 000 simulations using the prespecified TV value, and NoGo and Futility definitions.

A false NoGo is defined as observing either futility criteria during the continuous monitoring stage or NoGo criteria at final analysis when the true ORR is greater than or equal to the TV (ie, False NoGo: P[Futility or NoGo Decision | True ORR ≥ TV]).

Table 7-3. Guidelines for Futility Analysis

True ORR (BM ORR = 12%)	Probability of Futility	Expected N	% Decision Prior to Final
10%	96%	29	67%
15%	76%	35	35%
20%	44%	38	14%
25%	19%	39	5%
30%	6%	40	1%
35%	1%	40	0%

Date: 24 March 2023 Page 31 of 53

40%	0%	40	0%
-----	----	----	----

BM ORR = benchmark objective response rate; TV = target value.

Criteria: TV = 30%; NoGo: Pr(ORR > TV) < 5%; Futility: PP(NoGo) > 95%;

Frequency: 10 subjects.

